5.11 Handling of Partial Dates for Other Data

Other data with partial dates will be listed as collected. For calculations of time intervals listed [REDACTED] below, the dates will be imputed with the first day of the month (if the day is missing) or with January 1 (if both day and month are missing). If additional imputation is required, instructions will be provided in future amendments to this document.

5.12 Handling of Missing Data

Missing data will not be imputed, except for:

- Missing date parts, i.e., partial dates, discussed above.
- [REDACTED]
- Missing AE relationship to study drug [REDACTED].

6. STUDY SUBJECTS

6.1 Subject Enrollment

The number of subjects in each analysis set will be summarized for all patients. Analysis set flag for each subject will be listed together with the dose level and dose schedule for all patients.

6.2 Subjects Disposition

Subjects disposition will be summarized by dose level and dose schedule if applicable, and overall for the Safety Population including:

- Number of subjects treated in each safety [REDACTED] and DLT population.
- Number of subjects treated.
- Number of subjects who discontinued study treatment and primary reasons of discontinuation.
- Number of subjects who completed the study.
- Number of subjects who discontinued study and primary reasons of discontinuation by analysis population.

The primary reason for treatment discontinuation and study discontinuation will be summarized by categories in eCRF. Subjects' disposition will be listed for the Safety Population.

6.3 Protocol Deviations

Important protocol deviations are protocol deviations that may have significant impact on a patient's rights, safety, or well-being, or compromise the analysis and interpretation for the primary study endpoints. Protocol deviations will be identified and classified ongoing basis based on the protocol deviation plan and finalized prior to any database snapshot or database lock. Only important protocol deviations will be listed in a CSR for the Safety Population.

6.4 Demographics and Other Baseline Disease Characteristics

Demographic and baseline characteristics will be tabulated using descriptive statistics for the Safety Population. The following variables will be included:

- Age at Consent (years)
- Sex at birth
- Race
- Ethnicity
- Height (cm)
- Weight (kg)
- BMI (body mass index, kg/m²), defined as weight (kg) / height (m)²
- ECOG at Screening
- Genotype (BRCA1, BRCA2, PALB2, etc.)

- Tumor types (Prostate adenocarcinoma, Pancreatic adenocarcinoma, breast carcinoma, Ovarian epithelial carcinoma)
- Histology Grade of disease at diagnosis (G1, G2, G3, G4, Gx, unknown, Other).
- Country of study site.

The below baseline disease characteristics may be further summarized (if applicable to majority of patients) or included in the subject listing:

- Time from initial diagnosis to first dose (Months) and time from diagnosis at Screening to first dose (Months), calculate as (Date of Informed Consent – Date of diagnosis + 1)/30.4375
- Molecular features (AR-V7, Other AR variant, Unknown, Other)
- Tumor primary location (Ovaries, Peritoneum, Fallopian tube, Multiple sites/Unknown)
- Histology Categories (Ductal carcinoma, Lobular carcinoma, High Grade serous, Low grade serous, endometrioid, clear cell, mucinous, Other)
- Genotypes (BRCA1, BRCA2, PALB2, RAD51B/C/D, HRD/GIS Positive+)
- ER status (Positive, Negative)
- PR status (Positive, Negative)
- HER2 Status:
 - Positive (IHC3+ or IHC2+/ISH+)
 - Low (IHC1+ or IHC2+/ISH-)
 - Negative (IHC0)
- Time from diagnosis of disease to metastasis (months), calculated as (Date of diagnosis for metastatic disease – Date of diagnosis + 1)/30.4375

Conversions for height and weight are as follows:

Height (cm) = Height (inches) x 2.54

Weight (kg) = Weight (lb) x 0.4536

Demographics and baseline disease characteristics will be tabulated and listed in the Safety Population set.

6.1 Prior Anti-Cancer Systemic Therapy

Prior Anti-cancer systemic therapy will be summarized, including

- Prior systemic therapy (Yes, No)
- Number of lines of prior systemic therapy
- Prior platinum
- Prior PARP inhibitor
- Time from the most recent prior systemic therapy to the first dose of the study drug (months), calculated as: (Date of first dose of study drug – End date of last prior systematic therapy +1)/30.4375
- Best overall response (BOR) from last prior systemic therapy

- Reason for therapy ended from last prior systemic therapy (Completion of therapy as planned, Progressive Disease, Toxicity, Other)

Prior anti-cancer systemic therapy will be summarized and listed for Safety Population.

6.2 Prior Anti-Cancer Radiotherapy

Prior Anti-cancer radiotherapy will be listed, including

- Reason for Administration
- Time from most recent radiotherapy to first dose of the study drug (months), calculated as: (Date of first dose of study drug – End date of most recent prior radiotherapy+1)/30.4375

Prior anti-cancer radiotherapy will be listed for Safety Population.

6.3 Medical History

Medical history will be coded using the Medical Dictionary for Regulatory Activities (MedDRA) version 27.0.

The frequency count and percentage of subjects experiencing any medical conditions will be tabulated by System Organ Classifications (SOC) and Preferred Term (PT). If a Preferred Term or System Organ Class was reported more than once for a subject, the subject would only be counted once in the incidence for that preferred term or system organ class.

Medical history data will be summarized for the Safety Population.

6.4 Prior and Concomitant Medications

Prior and concomitant medications will be coded using the World Health Organization Drug (WHODrug) Dictionary version March 2024. Unless specified otherwise, summaries of prior and concomitant medications will be presented by Anatomical Therapeutic Class (ATC) Level 2 and Preferred Term with numbers and percentages for subjects in the Safety Population.

A subject who takes more than one medication will be counted only once if these medications belong to the same ATC Level 2 classification.

In the summary tables, prior medications and concomitant medications will be presented by decreasing frequency of subjects overall within each ATC Level 2 class and then similarly by decreasing frequency of subjects overall within each preferred term. In the case of ATC Level 2 classes or preferred terms with equal frequencies, medications will be sorted alphabetically.

Prior medications are defined as those medications that stopped prior to the first administration of the study drug. Concomitant medications/procedures are defined as those medications taken on or after the first administration of the study drug till 30 days after the last dose of study treatment, or the start of subsequent anticancer therapy, whichever occurs first.

A prior medication could also be classified as "both prior and concomitant medication/procedure" if the end date is on or after first dose of study treatment. In the listing, it will be indicated whether a medication is prior-only, concomitant-only, or both prior and concomitant medication.

6.5 Concomitant Procedures

Concomitant procedures will be coded using the Medical Dictionary for Regulatory Activities (MedDRA) version 27.0. Unless specified otherwise, summaries of concomitant procedures will be presented by System Organ Classifications (SOC) and Preferred Term (PT) with numbers and percentages for subjects in the Safety Population. If a Preferred Term or System Organ Class was reported more than once for a subject, the subject would only be counted once in the incidence for that preferred term or system organ class.

In the summary tables, concomitant medications will be presented by decreasing frequency of subjects overall within each System Organ Class and then similarly by decreasing frequency of subjects overall within each preferred term. In the case of System Organ classes or preferred terms with equal frequencies, procedures will be sorted alphabetically. Transfusions and administration of growth factors will be listed separately.

6.6 Drug Exposure and Compliance

RP-3467 and olaparib (if applicable) exposure will be summarized and grouped by dose level and dose schedule within arm 1 (monotherapy) and arm 2 (combination therapy) respectively, for overall treatment period for the Safety Population by the following parameters for both RP-3467 and olaparib if applicable:

- Duration of treatment (weeks)
- Number of cycles with a non-zero dose
- Any dose interrupted
- Any dose reductions
- Any dose increase
- Actual cumulative dose (in cycle 1 and overall)
- Relative dose intensity (in cycle 1 and overall treatment period)

For duration of treatment (weeks), actual cumulative dose, dose intensity, the number of observations (n), mean, standard deviation, median, minimum, and maximum will be provided as summary statistics. For dose interruptions and modifications, the frequency and percentage in each category will be provided.

6.6.1 Duration of Treatment

Duration of treatment will be calculated separately for RP-3467 and olaparib. Duration of treatment will be calculated as:

Duration of treatment of RP-3467 or olaparib (weeks) = (min (last dose date of RP-3467 or olaparib respectively; death date; data cutoff date) – treatment start date +1)/7

For participants who have discontinued study treatment, the last dose date will be used as the treatment end date. For participants with ongoing treatment at the time of data extraction, the data cutoff date will be used.

If a participant has a recorded date of death that precedes both the last dose date and the data cutoff date, and it cannot be corrected after querying the issue, the date of death will be used as the treatment end date.

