In Arm 1, eligible participants will be treated with escalating doses of RP-3467 monotherapy, preceded by a 2-day PK run-in, to evaluate the safety and tolerability, PK, and pharmacodynamics of RP-3467 monotherapy. The cycle length will be 21 days. Evaluation of escalating doses of RP-3467 in combination with olaparib in Arm 2 will occur in parallel with Arm 1. The starting RP-3467 dose for the combination in Arm 2 will be at least one dose level lower (DL-1) than the highest monotherapy dose level evaluated and considered tolerated/safe by the Safety Review Committee (SRC).

Following disease progression, participants in the monotherapy arm will have the opportunity to receive the combination of RP-3467 and olaparib at the highest previously evaluated dose level of the combination deemed safe and tolerable (or at the preliminary RP2D if previously determined), provided they meet all required eligibility criteria, have not had Grade >2 drug-related toxicities at their current monotherapy dose, and following discussion with and approval by the Medical Monitor.

A starting Arm 1 dose level of 160 mg once daily (QD) for RP-3467 monotherapy was chosen based on preclinical Good Laboratory Practice (GLP) safety data. *In vitro* data suggest RP-3467 may be a weak cytochrome P450 (CYP) 3A inhibitor and inducer; thus, due to an unclear potential for drug-drug interactions (DDI) and confounding toxicities from olaparib alone, a starting dose of 200 mg twice daily (BID) olaparib, a lower dose than the United States Prescribing Information (USPI) recommended dose of 300 mg BID, will initially be evaluated in Arm 2 (DL-1a). Once safety and tolerability of the combination is confirmed and PK data reviewed from the initial Arm 2 cohort(s), the olaparib dose may be increased to 300 mg BID for subsequent cohorts (e.g., DL-1b).

Dose escalation and de-escalation decisions will be based on Boin criteria. The decision to escalate either RP-3467 or olaparib following the first dose level of Arm 2 will be based on [REDACTED] safety data and agreed upon by the SRC. The exposure of olaparib and RP-3467 from the first combination cohort in Arm 2 will be evaluated and used to inform the dose selection of the next combination dose level. Specifically, the RP-3467 dose will be escalated to a level that is not expected to exceed the exposure of the dose of RP-3467 monotherapy which has been cleared by the SRC. [REDACTED]

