[REDACTED] During the dose escalation phase, initially up to 3 participants will be treated at each monotherapy dose level in Arm 1, and 3 participants will be treated at each combination dose level in Arm 2. In addition to satisfying Boin criteria, to initiate each dose level in Arm 2, a higher RP-3467 dose level must have been previously tested in Arm 1 and cleared by the SRC.

In Arm 1, RP-3467 may be escalated in increments of 100% until dose level N is reached, defined as follows:

- Any Grade ≥ 3 hematological toxicity, or
- $>50\%$ decrease in platelets or neutrophils from the first dose, or
- >2 g/dL decrease in hemoglobin from the first dose, or
- Any \geq Grade 2 drug-related non-hematological toxicity lasting >5 days or requiring clinical intervention, except Grade 2 fatigue, nausea, vomiting, diarrhea, or constipation, or
- Adverse event (AE) of any grade limiting tolerability as assessed by the SRC.

After dose level N is reached, subsequent dose levels will evaluate RP-3467 dose increases of up to 75%, as determined by the SRC, which based on the safety profile observed, may be guided by a modified Fibonacci sequence (up to 67%, 50%, and 33%) in consecutive cohorts per SRC discretion.

Dose escalations of RP-3467 in Arm 2 will be guided by the dose levels established in Arm 1. The same triggers as for Dose level N in Arm 1 will trigger reduced dose escalation increments in Arm 2 if the events occur during the DLT evaluation period (from the start of first dose through the end of Cycle 1). Thus, in the setting of combination-specific toxicities, the RP-3467 dose in Arm 2 may be lower than at the corresponding dose level in Arm 1. Intermediate dose levels of RP-3467 can be evaluated if recommended by the SRC.

Dose Level	Arm 1		Arm 2	
	RP-3467 Daily (mg) ^a or % of previous dose	RP-3467 Daily (mg) ^a	Olaparib (mg, BID)	
-1a			200	
-1b ^b	NA	80	300 ^b	
1	160		300	

Dose Level	Arm 1	Arm 2	
	RP-3467 Daily (mg)^a or % of previous dose	RP-3467 Daily (mg)^a	Olaparib (mg, BID)
2	Up to 100% increase until level N	RP-3467 dose no higher than corresponding Arm 1 DL	300
N+1	≤75% increase (per SRC, guided by modified Fibonacci)		300

BID = twice daily; DL = dose level; NA = not applicable; PK = pharmacodynamics; QD= daily; SRC = safety review committee

^a Initially, a QD regimen will be evaluated for RP-3467.

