5.2 Definition of Treatment Emergent Period

Unless otherwise stated, derivations of the worst post-treatment value will be assessed within the confines of the treatment emergent period, defined as the time from the start of study treatment, until 30 days after the last dose of RP-3467 or olaparib, the participant starts a subsequent anti-cancer therapy, or the participant is taking the monotherapy treatment and starts olaparib treatment, whichever occurs first.

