5.3 Definition of Resue Period

For rescue arm patients who have been crossed over to the protocol-defined rescue treatment (combination therapy after treatment with monotherapy), the rescue period is defined as the time between the first dose of the co-therapy olaparib to study treatment discontinuation.

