6.6.2 Dose Reduction

Dose reduction is defined as 1) decreased in the total daily dose level or, 2) a decrease in the frequency of dosage (BID to QD for example)

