6.6.4 Actual Cumulative Dose

The actual cumulative dose of RP-3467 or olaparib is defined as the sum of all actual doses administered taking into consideration of any dose change during the study treatment exposure. Information on dose modifications, including dose increases, reductions, and interruptions will be recorded in the CRF. Modifications will be recorded with their start and end dates, as well as the reason for dose change, this information will be used to determine the total cumulative dose over the course of treatment exposure.

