6.6.6 Relative Dose Intensity

[figure not shown]
The Relative Dose Intensity (RDI) is defined as the ADI divided by Planned Dose Intensity (PDI) and reported as Percentage. The PDI is defined as the initial dose of the study drug multiplied by planned number of dosing days per cycle according to the protocol. The planned cycle length (days) is 21 days. Initial dose is the dose per day which was intended to be administered at the start of the planned dose regimen. For RDI will be summarized for Cycle 1, as well as across the entire treatment period. Subjects that crossed over from monotherapy to combination therapy, RDI is only calculated up to the start of the rescue treatment period.

[figure not shown]
Details of study treatment exposure will be listed for Safety Population and swimmer plot for duration of treatment for individual participants by arm, dose level, and dose schedule will be presented.

10.SAFETY ANALYSIS

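### Except for relative dose intensity, the Arm 1 exposure measures are not cut at crossover, so for participants who cross over they mix monotherapy with combination treatment

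*SAP*

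**What the plan says.** Crossover is part of the design. Under Protocol 1.1 (Overall Design), after progression "participants in the monotherapy arm will have the opportunity to receive the combination of RP-3467 and olaparib", provided they meet the eligibility criteria, have had no drug-related toxicity above Grade 2 at their monotherapy dose, and have Medical Monitor approval. SAP 5.3 names the time that follows: "the rescue period is defined as the time between the first dose of the co-therapy olaparib to study treatment discontinuation". Rescue dosing is therefore still study treatment.

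SAP 6.6 summarises exposure within each arm, with Arm 1 labelled as monotherapy, over the whole treatment period. The component rules are:

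- Duration (6.6.1) ends at the earliest of the last dose of the drug, death or data cutoff. "For participants who have discontinued study treatment, the last dose date will be used as the treatment end date".
- Cumulative dose (6.6.4) is the "sum of all actual doses administered taking into consideration of any dose change during the study treatment exposure".
- Reduction (6.6.2): "Dose reduction is defined as 1) decreased in the total daily dose level", or a lower dosing frequency. Increase (6.6.3) is the mirror image.
- Number of cycles and interruptions are listed in 6.6 with no end point of their own.

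Only one exposure measure has a crossover rule, in 6.6.6: "Subjects that crossed over from monotherapy to combination therapy, RDI is only calculated up to the start of the rescue treatment period". Outside the exposure section, the treatment-emergent period in 5.2 ends at several events, the last being "or the participant is taking the monotherapy treatment and starts olaparib treatment, whichever occurs first". The TEAE definition in 10.2 has the same stop, but RP-3467-related SAEs count whenever they occur.

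**The concern.** RP-3467 continues during rescue, so its last dose falls in the rescue period. A programmer following 6.6.1 to 6.6.4 would credit rescue weeks and rescue milligrams to the participant's original monotherapy dose level. Within one table, the relative dose intensity (RDI) row would cover monotherapy, while the duration, cycle, cumulative-dose and dose-change rows would cover monotherapy plus combination.

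The switch itself can also be counted. To open an Arm 2 level, Protocol 1.1 requires that "a higher RP-3467 dose level must have been previously tested in Arm 1 and cleared by the SRC". Every combination level therefore carries less RP-3467 than the highest cleared monotherapy level. A participant on that highest level who crosses over must move to a lower RP-3467 dose. That meets the 6.6.2 definition of a reduction although no toxicity prompted it. A participant on a lower level might move up and arguably count under 6.6.3.

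What is at stake is the description of how long, and with what dose changes, RP-3467 alone was given. Readers set that description beside the Arm 1 adverse event tables, and most of those tables stop at the first olaparib dose.

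**Working it through.** The plan states no figure to reproduce, so the check applies its definitions to a worked case.

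**Step 1: where each Arm 1 measure stops for a crossover participant**

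| Measure | SAP section | Stops at first olaparib dose? |
|---|---|---|
| Duration of RP-3467 | 6.6.1 | No |
| Cycles, interruptions | 6.6 | No |
| Reductions, increases | 6.6.2, 6.6.3 | No |
| Cumulative dose, overall | 6.6.4 | No |
| Actual dose intensity (ADI) | 6.6.5 | Not stated |
| RDI | 6.6.6 | Yes |
| Worst post-treatment values | 5.2 | Yes |
| TEAEs | 10.2 | Yes, except RP-3467-related SAEs |

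Section 5.2 governs worst post-treatment values and does not reach the exposure measures.

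**Step 2: inputs**

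- From the documents: 21-day cycle; Arm 1 of about 12 participants (SAP 2.3); 160 mg and 80 mg daily as entries in the dose-level table.
- Assumed, for arithmetic only: continuous daily dosing; 12 weeks of monotherapy at 160 mg; rescue at 80 mg for 6, 12 or 24 weeks; 2, 4 or 6 of 12 participants crossing over.

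**Step 3: one participant**

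- Duration = (last RP-3467 dose − start + 1)/7. With a cut at the first olaparib dose it is 12 weeks. As written it is 12 + 6, 12 + 12 or 12 + 24, that is 18, 24 or 36 weeks.
- Cumulative dose with the cut = 160 × 84 = 13,440 mg. As written, add 80 × 42, 80 × 84 or 80 × 168, giving 16,800, 20,160 or 26,880 mg (ratios 1.25, 1.5 and 2.0).
- Planned dose intensity = 160 × 21 = 3,360 mg per cycle. RDI with its cut = (13,440/4)/3,360 = 100%.
- The same formula on the uncut rows gives (16,800/6)/3,360 = 83%, (20,160/8)/3,360 = 75% and (26,880/12)/3,360 = 67%. The table would print 100% beside a duration and cumulative dose that imply 83%, 75% or 67%. The mismatch arises whenever RP-3467 intensity in rescue differs from that in monotherapy.

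**Step 4: Arm 1 overall column (n = 12)**

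Mean duration = 12 + (crossovers × rescue weeks)/12, against 12 weeks with the cut.

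| Crossovers | 6 weeks | 12 weeks | 24 weeks | Reductions added if every switch lowers the dose |
|---|---|---|---|---|
| 2 | 13 | 14 | 16 | 2/12 = 16.7% |
| 4 | 14 | 16 | 20 | 4/12 = 33.3% |
| 6 | 15 | 18 | 24 | 6/12 = 50.0% |

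The last column is an upper bound, since not every switch need lower the dose. The median stays at 12 weeks with 2 or 4 crossovers. With 6 it is the midpoint of 12 and 12 + rescue weeks, which equals the mean.

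**Step 5: one three-person cohort**

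Take monotherapy of 6, 12 and 12 weeks, with one participant adding 18 rescue weeks. The mean goes from (6 + 12 + 12)/3 = 10 to (6 + 12 + 30)/3 = 16 weeks. The median stays at 12. If that switch lowers the dose, reductions go from 0/3 to 1/3 (33.3%).

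**The case against.** The strongest reply is that this is a wording gap in descriptive tables that no decision depends on. Much of that stands:

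- **Primary endpoints.** A reader might infer that the Arm 1 safety results are contaminated. The documents do not support that. DLTs are confined to Cycle 1, MTD selection rests on DLT rates, and TEAEs leading to dose reduction, interruption or withdrawal stop at olaparib start. A planned switch is not an adverse event and cannot enter those rows. Cycle 1 dose summaries are untouched unless progression falls within Cycle 1.
- **Reach.** It is tempting to say that all 12 or so Arm 1 participants could cross over and that a few would shift every row. Crossover is conditional, and each case alters only its own dose-level row and the overall column.
- **Adverse events.** Nor is it exact to set mixed exposure against purely monotherapy TEAEs, because RP-3467-related SAEs in rescue are counted.
- **Traceability.** Reasons for dose changes are recorded, and exposure listings and a swimmer plot are planned, so a careful reader could separate a crossover switch from a toxicity reduction. Section 6.6.3 also links increases to intraparticipant escalation, so counting an upward switch there is open to argument.
- **Missing text.** The public SAP passes from 6.6.6 to Section 10. A separate rescue summary elsewhere cannot be excluded.

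Total RP-3467 exposure is also a legitimate quantity. What the reply does not answer is that the tables label it monotherapy, that one row of the same table stops at crossover and the others do not, and that 6.6.1, 6.6.2 and 6.6.4 show no redaction that could hide such a rule.

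**Conclusion.** The point holds as an internal inconsistency in the exposure derivations. The SAP never says outright that rescue time counts towards Arm 1. That follows from the formulas, from 5.3 treating rescue as study treatment, and from the crossover cut being written for RDI alone among the exposure measures. For each participant who crosses over, the monotherapy rows for that dose level and the Arm 1 overall column would include combination treatment, and a switch to a lower RP-3467 dose would be scored as a reduction.

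The size cannot be fixed from the documents, which give neither the number of crossovers nor the length of rescue. Under the stated assumptions a crossover participant's duration is overstated by 50% to 200% (18 to 36 weeks against 12), and the Arm 1 mean by 1 to 12 weeks. Medians move less unless about half the arm crosses over. It should be corrected before the exposure tables are programmed; it does not threaten the dose-finding conclusions.

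**What to change.** In SAP 6.6 to 6.6.5:

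1. For Arm 1 participants who cross over, end the exposure period on the day before the first olaparib dose for duration, cycles, cumulative dose, ADI, interruptions, reductions and increases, in line with 6.6.6.
2. State that the change of RP-3467 dose made at crossover is not counted as a reduction or an increase.
3. Summarise RP-3467 and olaparib exposure in the rescue period (5.3) as a separate block, if this is not already specified elsewhere, and mark the crossover date on the swimmer plot.

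The cost is a few sentences of SAP text and one extra exposure block. Dose modifications and their dates are already recorded, so no new data are needed. Arm 1 durations will look shorter, and total RP-3467 exposure will have to be read from two blocks together.
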